8.1.1. Baseline Procedures

8.1.1.1. Medical History

Medical history, COVID-19 disease history and SARS-CoV-2 tests results if available, and demographics will be collected at screening. Smoking status will be collected. Complete medication history of all prescription or nonprescription drugs (including vaccinations), and dietary and herbal supplements taken within 30 days prior to the planned first dose will be collected. COVID-19 vaccinations, antiviral and monoclonal antibody treatment for the treatment of COVID-19 at any time prior to the planned first dose will also be collected.

Risk factors for the participant developing severe COVID-19 illness will be recorded.

8.1.1.2. Secondary Contacts

At baseline and as noted in the [SoA](#), the investigator will collect contact information for at least 2 individuals who can be contacted if the participant cannot be reached after multiple attempts. Secondary contacts may be used to determine if a participant is lost to follow-up or vital status check.

8.1.2. Household Characteristics

Household characteristics will be determined through interview with the study participant and will be updated during the study. The household characteristics include:

- Number of people living in household;
- Number of additional confirmed SARS-CoV-2 positive or suspected (ie, symptomatic) household members and date of confirmed or suspected SARS-CoV-2.

8.1.3. Telehealth Visits

Telehealth visits may be used to assess participant safety and collect data points. Telehealth includes the exchange of healthcare information and services via telecommunication technologies (eg, audio, video, videoconferencing software) remotely, allowing the participant and the investigator to communicate on aspects of clinical care, including medical advice, reminders, education, and safety monitoring. The following assessments must be performed during a telehealth visit (see the [SoA](#)):

- Review and record study intervention(s), including compliance and missed doses.
- Review and record any AEs and SAEs since the last contact. Refer to [Section 8.4](#).
- Review and record any new concomitant medications or changes in concomitant medications since the last contact.
- Review and record contraceptive method and results of pregnancy testing. Confirm that the participant is adhering to the contraception method(s) required in the protocol. Refer to [Appendix 4](#).

Study participants must be reminded to promptly notify site staff about any change in their health status.

Observe (ie, video, videoconferencing software) the participant performing the rapid antigen test (participant self collected rapid antigen test), if the procedure is conducted remotely, and record the results for offsite visits in accordance with the [SoA](#).

8.1.4. Home Health Visits

A home health visit may be utilized to facilitate scheduled visits. Home health visits include a healthcare provider conducting an in-person study visit at the participant's location, rather than an in-person study visit at the site. The following may be performed during a home health visit (see the [SoA](#)):

- Review and record study intervention(s), including compliance and missed doses.
- Review and record any AEs and SAEs since the last contact. Refer to [Section 8.4](#).

- Review and record any new concomitant medications or changes in concomitant medications since the last contact.
- Review and record contraceptive method and results of pregnancy testing. Confirm that the participant is adhering to the contraception method(s) required in the protocol. Refer to [Appendix 4](#).
- Collect clinical laboratory and biomarker samples.
- Observe rapid antigen testing, record result, and collect NP/OP swab samples.
- Collect vital signs.
- Confirm the participant has completed the PRO assessments.
- Retrieve unused study intervention and empty study intervention containers
- Collect/update secondary contacts
- Collect/update household characteristics
- Collect COVID-19-related medical visits
- Collect COVID-19 adjunctive therapeutic procedures
- If the HCP is unable to collect AEs, concomitant medications, the site should contact the participant via a follow-up telephone call to collect the additional information.

It is recommended that the investigator discuss temporary or permanent discontinuation of study intervention with the study medical monitor.

8.2. Efficacy Assessments

8.2.1. Participant Diary

Participants will be provided an electronic handheld device or will use their own device to record study intervention administration, signs and symptoms of COVID-19, and PRO assessments in the study diary.

Participants will receive daily reminders to complete entries on their own as specified in the [SoA](#). The diary should be completed at approximately the same time every day. Staff will review the participant's study diary online as specified in the [SoA](#).

The diary allows recording of these assessments only within a fixed time window (next calendar day), thus providing an accurate representation of the participant's experience at that time. The participant is able to make revisions to incorrect entries before pressing the save or submit button. In the event that a participant becomes aware of an error in data after the entry is saved, a change to the diary data may only be made by the investigator submitting a data clarification form. Data reported in the participant diary will be transferred

electronically to a third-party vendor, where they will be available for review by investigators and the sponsor or delegate at all times via an internet-based portal.

8.2.2. COVID-19-Related Medical Details

Details of participants' COVID-19-related medical visits will be collected. These are hospitalization of any duration, urgent care, emergency room ≤ 24 h, practitioner's office, telemedicine, home health care services or extended care facility stay and will be collected during study visits, including level of care (ICU status) and dates of utilization, including admission and discharge, as applicable.

Hospitalization >24 hours is defined as >24 h of acute care in a hospital or similar acute care facility, including Emergency Rooms or temporary facilities instituted to address medical needs of those with severe COVID-19. This includes specialized acute medical care unit within an assisted living facility or nursing home. This does not include hospitalization for the purposes of public health and/or clinical trial execution.

8.2.3. PRO Assessments

PRO assessments will be recorded in the study eDiary.

8.2.3.1. Global Impression Questions

Three questions will be included in the ePRO to assess patient-reported global impression items: a) return to usual health; b) return to usual activities; and c) overall COVID-19-related symptoms[17]. For participants who report COVID-19 symptoms in the diary, the global impression questions will be answered after the completion of the COVID-19 signs and symptoms diary is completed.

8.2.3.2. SF-36 v2® Health Survey (Acute Form)[18]

Only adult study participants ≥ 18 years of age at the time of screening will be asked to complete the SF-36 at the timepoints indicated in the [SoA](#).

SF-36 v2® Health Survey (the acute form) is a 36-item questionnaire that measures functional health and well-being from a patient's perspective over a 1-week recall period. It is a generic questionnaire and can be used across age (adults), disease, and treatment groups. The questionnaire consists of 8 health domain scales: physical functioning (10 items), role physical (4 items), bodily pain (2 items), general health (5 items), vitality (4 items), social functioning (2 items), role-emotional (3 items), mental health (5 items), reported health transition (1 item) and 2, physical and mental component summary scores. Each health domain scale raw score is transformed to 0-100 scale which can then be converted to norm based T-scores (Mean=50, SD=10). SF-36 v2® Health Survey will be completed as specified in the [SoA](#).

8.2.3.3. WPAI

Only adult study participants ≥ 18 years of age at the time of screening will be asked to complete the WPAI at the timepoints indicated in the [SoA](#).

COVID-19 impacts manual and office-based work, and results in missed work due to illness or quarantine and loss of productivity [19]. The WPAI-GH is being implemented for COVID 19 (ie, WPAI-COVID-19) in order to evaluate change from baseline in work burdens. The WPAI-GH has demonstrated validity, reliability and sufficient predictive value to measure the impact of disease on absenteeism, presenteeism, and overall productivity in a manner that can also be monetized [20].

The WPAI-COVID-19 consists of 6 questions that refer to the following assessments for work productivity: 1 = currently employed, 2 = hours missed due to health problems, 3 = hours missed for other reasons, 4 = hours actually worked, 5 = degree health affected productivity while working (using a 0 to 10 VAS), and 6 = degree health affected productivity in regular unpaid activities. The recall period for questions 2 through 6 is 7 days. Four main outcomes will be generated from the WPAI-COVID-19 and reported as: 1) percent work time missed due to COVID-19 for those who are currently employed, 2) percent impairment while working due to COVID-19 for those who are currently employed and actually worked in the past 7 days, 3) percent overall work impairment due to COVID-19 for those who are currently employed, and 4) percent activity impairment due to COVID-19 for all respondents [20]. The WPAI-COVID-19 will be completed as specified in the [SoA](#).

8.2.3.4. EQ-5D-5L Scale

Only adult study participants ≥ 18 years of age at the time of screening will be asked to complete the EQ-5D-5L at the timepoints indicated in the [SoA](#).

The EQ-5D is a validated, standardized, generic instrument that is a preference-based health related quality of life questionnaire in cost effectiveness and HTA[21-23]. Recently, a version was developed called EQ-5D-5L with 5 response levels on each dimension compared to the 3 response levels in the EQ-5D-3L[21-27].

Measurement properties of the EQ-5D-5L demonstrated to be a valid version of the 3 level questionnaire that improved measurements by adding discriminatory power, reducing the ceiling, and establishing convergent and known groups validity[21,23,25,26]. Both the EuroQol EQ-5D-3L and EQ-5D-5L versions are well established instruments used to measure health states and utilities in various diseases areas and assess mobility, self-care, usual activities, pain/discomfort, anxiety/depression and health status using a VAS[24,28]. The EQ-5D-5L should be completed as described in the [SoA](#).

8.2.3.5. COVID-19 Signs and Symptoms

On Day 1, participants will complete the COVID-19 signs and symptoms ([Appendix 11](#)) in the study diary, before receiving study intervention. Participant assessment of COVID-19-related symptoms should be recorded at approximately the same time each day as specified in the [SoA](#) and as described in [Appendix 11](#).

COVID-19-related symptoms will be evaluated in accordance with FDA guidelines. Participants will record a rating of their symptom severity over the past 24 hours based on a 4-point scale in which 0 is reported if no symptoms were present; 1 if mild; 2 if moderate; and 3 if severe.

Vomiting and diarrhea will each be rated on a 4-point frequency scale where 0 is reported for no occurrence, 1 for 1 to 2 times, 2 for 3 to 4 times, and 3 for 5 or greater.

Sense of smell and sense of taste will each be rated on a 3-point Likert scale where 0 is reported if the sense of smell/taste was the same as usual, 1 if the sense of smell/taste was less than usual, and 2 for no sense of smell/taste.

During the long-term follow-up period as noted in the [SoA](#), site staff will ask participants if they have experienced pre-defined COVID-19 signs and symptoms or other symptoms believed to be related to COVID-19, over the past 7 days, including the day of the study visit. For each sign or symptom reported, the worst severity (mild, moderate or severe) during the past week should be recorded in the CRF.

8.3. Safety Assessments

Planned time points for all safety assessments are provided in the [SoA](#). Unscheduled safety measurements may be obtained at any time during the study to assess any perceived safety issues.

8.3.1. Targeted Physical Examination, Height and Weight

Physical examination is to be completed before administration of study intervention.

A targeted physical examination will include, at a minimum, cardiopulmonary assessments. Height and weight will also be measured and recorded at screening, though height may be self-reported for participants ≥ 18 years of age.

Physical examination findings collected during the study will be considered source data and will not be required to be reported, unless otherwise noted. Any untoward physical examination findings that are identified during the active collection period and meet the definition of an AE or SAE ([Appendix 3](#)) must be reported according to the processes in [Sections 8.4.1](#) to [8.4.3](#).

8.3.2. Vital Signs

Temperature, pulse rate, respiratory rate, oxygen saturation level, and blood pressure will be assessed as specified in the [SoA](#).

Any untoward vital sign findings that are identified during the active collection period and meet the definition of an AE or SAE ([Appendix 3](#)) must be reported according to the processes in [Sections 8.4.1](#) to [8.4.3](#).

8.3.2.1. Blood Pressure and Pulse Rate

BP and PR measurements will be assessed with the participant, preferably in the seated position with their feet on the floor when possible with a completely automated device[[29](#)]. It is recommended that the same position should be used for a participant throughout the study duration. Manual techniques will be used only if an automated device is not available.

8.3.2.2. Temperature and Respiratory Rate

Temperature and respiratory rate will be assessed.

8.3.2.3. Oxygen Saturation Level

Oxygen saturation level will be assessed as part of the vital signs assessment.

8.3.2.4. Point-of-Care Serum Creatinine Assessments

A serum creatinine point-of-care device will be used to assess kidney function as described in the [SoA](#) and [Appendix 7](#). If a serum creatinine point-of-care device assessment is performed at screening and baseline, the baseline estimate of kidney function will determine eligibility.

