Arm Title	Nirmatrelvir/ritonavir	Placebo/ritonavir
Arm Type	Experimental	Other
Arm Description	Participants will receive nirmatrelvir/ritonavir 300 mg/100 mg (or 150 mg/100 mg for participants with eGFR \geq 30 to $<$ 60 mL/min/1.73 m 2 or eCrCl \geq 30 to $<$ 60 mL/min) q12h from Day 1 through Day 5.	Participants will receive placebo 0 mg/ritonavir 100 mg q12h for 5 days.

Statistical Methods:

The study will randomize approximately 411 participants in a 2:1 randomization ratio to nirmatrelvir/ritonavir or placebo/ritonavir.

The primary efficacy endpoint is the change in viral SARS-CoV-2 RNA level from baseline to Day 5 as measured in NP swabs. This will be estimated without regard to study treatment discontinuation and without regard to prohibited therapies.

With respect to the primary endpoint of change in SARS-CoV-2 RNA level from baseline to Day 5 as measured in NP swab in the mITT analysis set, and assuming a SD of 1.8 (based on Study C4671005 [EPIC-HR, NCT04960202]), a sample size of approximately 315 evaluable participants (210 participants in the nirmatrelvir/ritonavir group and 105 participants in the placebo/ritonavir group) is expected to provide 90% power to detect a difference of 0.7 log₁₀ copies/mL in viral RNA between groups using a 2-sided 0.05 alpha level test. Assuming approximately 10% of participants will have a negative viral RNA result at baseline, and assuming a non-evaluable rate of 15%, approximately 411 participants will be randomized in the study to achieve approximately 315 participants evaluable for the primary efficacy endpoint.

No formal interim analysis is planned for this study. However, the sponsor may conduct unblinded reviews of the data during the course of the study if requested by regulatory

[figure not shown]
authorities including in the support of regulatory submissions. Should an unblinded review be requested, details of the unblinding plan will be described in the SAP and a separate data unblinding document.

Ethical Considerations:

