Abbreviations used in this table may be found in Appendix 12 .														
 Day relative to start of study intervention (Day 1). Baseline (Day 1) visit is a mandatory visit. Assessments indicated in brackets [X] are only to be conducted if indicated as described in the “Notes”.
Visit Window	Day -1 to Day 1	0 days	±1 day	±1 day	±1 day	±2 days	±2 days	±2 days	±3 days	±7 days	±7 days	±5 days		
 Screening procedures may be done from Day -1 to Day 1 and may be completed on the same calendar day as Baseline/Day 1 procedures. If screening and baseline visits are conducted on the same calendar day, assessments and procedure that are listed to occur at both visits only need to be completed once.
Laboratory Assessments														
 See Section 8.3.3 for additional information. See Appendix 2 for a list of Clinical Laboratory tests to be done. For laboratory collection volumes, see the laboratory manual.
Hematology		X		X					X			X		
 Baseline laboratory assessments should be collected prior to first dose of study intervention.
Blood chemistry		X		X					X			X		
 If deemed necessary to confirm eligibility, laboratory assessments at screening may be performed at the local laboratory at the investigator’s discretion. Abnormal laboratory valued related to AEs should be followed until resolution.
Point-of-care serum creatinine assessment	X	[X]												
 Screening visit: A serum creatinine point-of-care device assessment for determining estimation of kidney function (eGFR for adults 18 years and older, and eCrCl for adolescents 12 years to <18 years) is required for eligibility. See Section 10.7 for age specific kidney function calculations. Baseline visit assessment expected only if screening and baseline visits are held on different days. If a serum creatinine point-of-care device assessment is performed at

Table 1. Study Schedule of Assessment

Visit Identifier	Screen	Treatment Period				Efficacy and Safety Follow-up Period					LTFU			Notes	
		Baseline (Day 1)	Day 3	Day 5	Day 10	Day 15	Day 21	Day 28	Day 34	Week 12	Week 24	ET (prior to Day 34)			

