Abbreviations used in this table may be found in Appendix 12 .														
 Day relative to start of study intervention (Day 1). Baseline (Day 1) visit is a mandatory visit. Assessments indicated in brackets [X] are only to be conducted if indicated as described in the “Notes”. 	
Visit Window	Day -1 to Day 1	0 days	±1 day	±1 day	±1 day	±2 days	±2 days	±2 days	±3 days	±7 days	±7 days	±5 days		
 Screening procedures may be done from Day -1 to Day 1 and may be completed on the same calendar day as Baseline/Day 1 procedures. If screening and baseline visits are conducted on the same calendar day, assessments and procedure that are listed to occur at both visits only need to be completed once. 	
														
 screening and baseline, the baseline estimate of kidney function will determine eligibility. See Section 8.3.2.4. 	
FSH	X													
 FSH is to be performed locally to confirm postmenopausal status in female participants <60 years of age at screening who are not using hormonal contraception or hormonal replacement therapy. Female participants aged 50 to 60 years with no menses for 12 months do not need FSH testing to be performed to confirm postmenopausal status. See Appendix 2. 	
HIV test (Germany only)	X													
 Local HIV testing at screening will be performed for participants in Germany as required by the German HA See Appendix 2 See Section 8.3.4. 	
Pregnancy Test	X								X			X			
SARS-CoV-2 Serology		X		X				X				X			
Biomarker Assessments															
NP swab collection for SARS-CoV-2 RNA level		X	X	X	X	X	X	X	X			X		
 All NP swabs of both nares, will be collected by HCP at visits indicated. Samples will be shipped to central lab for quantitative SARS-CoV-2 RNA concentration. 	

Table 1. Study Schedule of Assessment

Visit Identifier	Screen	Treatment Period			Efficacy and Safety Follow-up Period						LTFU			Notes
		Baseline (Day 1)	Day 3	Day 5	Day 10	Day 15	Day 21	Day 28	Day 34	Week 12	Week 24	ET (prior to Day 34)		
Abbreviations used in this table may be found in Appendix 12 .														
 Day relative to start of study intervention (Day 1). Baseline (Day 1) visit is a mandatory visit. Assessments indicated in brackets [X] are only to be conducted if indicated as described in the “Notes”.

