Study intervention dispensation		X												
 Study intervention will be dispensed on Day 1. (See Section 6.1.1) See Appendix 7 for age-specific kidney function calculations to determine nirmatrelvir dosing.
Study intervention administration		Days 1 through 5												
 Baseline assessments should be performed before administration of the first study intervention. The first dose of study intervention will be administered to all participants on Day 1 during the in-person visit. All subsequent doses of study intervention will be self-administered (or administered to the participant by a legal guardian or caregiver). If only 1 dose of study intervention is administered on Day 1, study intervention should end on Day 6. See Section 6.1.
Participant-completed study intervention log		Daily on Days 1 through 5												
 Participants will use a participant-completed electronic dosing diary to record the date and time of their study intervention dosing. Study intervention log should be completed daily on Days 1 through 6 if only 1 dose was administered on Day 1. See Section 6.5.

Table 1. Study Schedule of Assessment

Visit Identifier	Screen	Treatment Period				Efficacy and Safety Follow-up Period					LTFU			Notes	
		Baseline (Day 1)	Day 3	Day 5	Day 10	Day 15	Day 21	Day 28	Day 34	Week 12	Week 24	ET (prior to Day 34)			
Abbreviations used in this table may be found in Appendix 12 .														
 Day relative to start of study intervention (Day 1). Baseline (Day 1) visit is a mandatory visit. Assessments indicated in brackets [X] are only to be conducted if indicated as described in the “Notes”. 	
Visit Window	Day -1 to Day 1	0 days	±1 day	±1 day	±1 day	±2 days	±2 days	±2 days	±3 days	±7 days	±7 days	±5 days		
 Screening procedures may be done from Day -1 to Day 1 and may be completed on the same calendar day as Baseline/Day 1 procedures. If screening and baseline visits are conducted on the same calendar day, assessments and procedure that are listed to occur at both visits only need to be completed once. 	
Staff review of study intervention log		Daily on Days 1 through 5												
 Staff review of the study intervention log should be completed daily on Days 1 through 6 if only 1 dose was administered on Day 1. See Section 6. 	

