6.1. Study Intervention(s) Administered

Study intervention will be self-administered by the participant OR administered to the participant by a legal guardian or caregiver.

A legal guardian or caregiver may administer study medication. Study personnel should review dose administration requirements with the participant, and, as appropriate, with the delegated caregiver(s) (may include school nurse) before administration and throughout the study as necessary.

Study Intervention(s)			
Intervention Name	Nirmatrelvir	Placebo for nirmatrelvir	Ritonavir
Arm Name (group of participants receiving a specific	nirmatrelvir/ritonavir	placebo	ritonavir

Study Intervention(s)			
treatment or no treatment)			
Type	drug	placebo	drug
Dose Formulation	tablet	tablet	capsule
Unit Dose Strength(s)	150 mg	0 mg	100 mg
Dosage Level(s)	300 mg q12h for 5 days 150 mg q12h for 5 days (for participants with eGFR \geq 30 to $<$ 60 mL/min/1.73 m ² (or eCrCl \geq 30 to $<$ 60 mL/min) at screening)	0 mg q12h for 5 days	100 mg q12h for 5 days
Route of Administration	Oral	Oral	Oral
Use	Experimental	Placebo	Experimental
IMP or NIMP/AxMP	IMP	IMP	IMP
Sourcing	Provided centrally by the sponsor. Refer to the IPM.	Provided centrally by the sponsor. Refer to the IPM.	Provided centrally by the sponsor. Refer to the IPM.
Packaging and Labeling	Study intervention will be provided in blister wallets. Each wallet will be labeled as required per country requirement. Products will be provided with blinded labels.	Study intervention will be provided in blister wallets. Each wallet will be labeled as required per country requirement. Products will be provided with blinded labels.	Study intervention will be provided in HDPE bottles. Each bottle will be labeled as required per country requirement. Products will be provided with open labels.
Current/Former Name(s) or Alias(es)	PF-07321332	NA	ritonavir

Study Arm(s)		
Arm Title	Nirmatrelvir/ritonavir	Placebo/ritonavir
Arm Type	Experimental	Other
Arm Description	Participants will receive nirmatrelvir/ritonavir 300 mg/100 mg (or 150 mg/100 mg for participants with	Participants will receive placebo 0 mg/ritonavir 100 mg q12h for 5 days.

	eGFR \geq 30 to $<$ 60 mL/min/1.73 m 2 or eCrCl \geq 30 to $<$ 60 mL/min) q12h from Day 1 through Day 5.	
Associated Intervention Labels	Nirmatrelvir/ritonavir	Placebo/ritonavir

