6.1.1. Administration

The first dose of study intervention will be administered at the site.

Nirmatrelvir 150 mg tablets or placebo for nirmatrelvir will be administered with ritonavir 100 mg for 5 days. Participants will be dispensed 1 blister wallet card of nirmatrelvir 150 mg tablets and 1 bottle of ritonavir capsules at the Day 1 site visit. Participants will be instructed to take:

- 2 tablets of nirmatrelvir 150 mg or placebo for nirmatrelvir q12h;
- 1 capsule of ritonavir 100 mg q12h.
 - Participants with moderate renal impairment (eGFR \geq 30 to $<$ 60 mL/min/1.73 m 2 [or eCrCl \geq 30 to $<$ 60 mL/min] at screening) will receive either 1 tablet of nirmatrelvir 150 mg and placebo for nirmatrelvir or 2 tablets of placebo for nirmatrelvir. The dose for ritonavir remains unchanged (ie, participants will receive 1 capsule of ritonavir 100 mg q12h).

Participants should take the first dose of study intervention on Day 1, during the in-person visit; that is, participants should take nirmatrelvir/placebo and ritonavir at the same time (no more than 15 minutes apart). The study intervention should be taken every 12 hours (\pm 4 hours), and not more than twice in a calendar day. Depending on the time of first dose, the timing of the second dose may be adjusted slightly to allow the participant/caregiver to select a convenient 12 hour dosing schedule as long as the next dose is taken at least 4 hours, but no later than 16 hours, after the first dose. Once the dosing schedule is adjusted, all subsequent doses should be taken every 12 hours (\pm 4 hours).

If a dose is delayed, it should be taken as soon as possible (but no later than 8 hours after the scheduled 12-hourly dose time), then resume the normal dosing schedule. If the participant misses a dose by more than 8 hours, the participant should not take the missed dose and instead take the next dose at the regularly scheduled time. The participant should not double the dose to make up for a missed dose. Dosing should be stopped at the end of the treatment period (Day 5 or 6). Any remaining tablets and/or capsules at the Day 5 visit should be returned. If the Day 5 visit is conducted prior to the last dose of study intervention (ie. Day 6), any remaining tablets or capsules should be collected at the next visit.

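### When creatinine is repeated on Day 1, the baseline value decides eligibility, but the written dose rules still tie the 150 mg nirmatrelvir tier to screening

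*Protocol*

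**What the plan says.** **Eligibility.** Screening may take place on Day -1 or Day 1. Table 1 (Section 1.3) provides for a second point-of-care creatinine: "Baseline visit assessment expected only if screening and baseline visits are held on different days". Where both exist, the Table 1 note says that for a test done at "screening and baseline, the baseline estimate of kidney function will determine eligibility". Section 8.3.2.4 repeats the rule: "the baseline estimate of kidney function will determine eligibility". Neither mentions dose.

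**Dose rules that name a visit.** There are two.
- The Dosage Level row of Section 6.1 gives 300 mg as standard and "150 mg q12h for 5 days (for participants with eGFR" or eCrCl of 30 to below 60, qualified as at screening.
- Section 6.1.1 sets the default at "2 tablets of nirmatrelvir 150 mg or placebo for nirmatrelvir q12h". It then says that participants with moderate renal impairment "at screening) will receive either 1 tablet of nirmatrelvir 150 mg" with a placebo tablet, or two placebo tablets.

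**Dose statements that name no visit.** The arm description in the synopsis (repeated in Section 6.1) reads "Participants will receive nirmatrelvir/ritonavir 300 mg/100 mg (or 150 mg/100 mg for participants with eGFR" in the reduced range. The Table 1 dispensing note refers to Appendix 7 for "age-specific kidney function calculations to determine nirmatrelvir dosing".

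**Other kidney provisions.** Exclusion 5 (synopsis and Section 5.2) applies the cut-off of 30 at screening. Section 7.1 acts on a post-screening value only if it is below 30. Section 6.6 makes dose modification not applicable. The SAP has no dose-tier rule.

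**The concern.** The protocol plans for two kidney-function readings before the first dose and ranks them for eligibility only. For dose, the literal text points to the older one. A participant can therefore be admitted on one reading and dosed on another that the protocol treats as superseded.

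At stake is how well the dose matches kidney function. Section 4.3 halves nirmatrelvir in moderate impairment because exposure is higher: the AUCinf ratio against normal function is 187.40% and the Cmax ratio 138.12%. These are group comparisons with normal function, so they overstate what is at stake for someone just below 60. The reverse pattern, 150 mg for a participant whose latest value is 60 or above, risks a lower dose than intended.

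**Working it through.** The plan states no figure to reproduce. The check has three parts.

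**1. What the text directs for each pair of readings**

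| Screening | Baseline | Eligible (Section 8.3.2.4) | Dose on active, read literally (6.1, 6.1.1) | Dose if baseline governed |
|---|---|---|---|---|
| 60 or above | 60 or above | yes | 300 mg | 300 mg |
| 30 to <60 | 30 to <60 | yes | 150 mg | 150 mg |
| 60 or above | 30 to <60 | yes | 300 mg | 150 mg |
| 30 to <60 | 60 or above | yes | 150 mg | 300 mg |

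The rules differ only in the last two rows. Participants on placebo take two placebo tablets in every row.

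**2. How small a change moves the tier**

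Appendix 7, man with creatinine above 0.9 mg/dL: eGFR = 142 × (Scr/0.9)^-1.200 × 0.9938^age. Take age 65 and assumed creatinine values.
- Scr 1.30: 142 × (1.4444)^-1.2 × 0.9938^65 = 61.0, the 300 mg tier.
- Scr 1.35: 142 × (1.5)^-1.2 × 0.9938^65 = 58.3, the 150 mg tier.

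A difference of 0.05 mg/dL near the cut-off is enough.

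**3. Illustration on assumed inputs**

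None of these inputs is in the documents. True eGFR is normal with mean 80 and SD 20, kept if 30 or above. Each reading carries independent lognormal error with SD 1.2 × creatinine CV (the exponent in the equation is -1.2). There were 4 million simulated draws.

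| | CV 3% | CV 5% | CV 8% |
|---|---|---|---|
| Screening ≥60, baseline 30 to <60 | 1.49% | 2.51% | 4.08% |
| Screening 30 to <60, baseline ≥60 | 1.50% | 2.52% | 4.10% |
| Either direction | 2.99% | 5.04% | 8.18% |
| × 2/3 (on active drug) | 1.99% | 3.36% | 5.45% |
| Wrong side of 60, stable function, by either value | 2.1% | 3.5% | 5.7% |
| True fall of 10%: wrong by screening / by baseline | 9.24% / 3.11% | 9.12% / 5.15% | 9.73% / 8.20% |
| True fall of 5%: wrong by screening / by baseline | 4.20% / 2.56% | 4.92% / 4.29% | 6.65% / 6.92% |

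The percentages are shares of participants tested on both days. With mean eGFR 90 the on-active share is 1.08% to 3.07%, and with mean 70 it is 2.93% to 7.74%.

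These shares are not wrong doses. Under measurement noise alone, 55% to 63% of those who cross downward truly have eGFR of 60 or above, and the two values misclassify equally often. The baseline value does better only if kidney function really moves. Even then, the gain disappears for a 5% fall at CV 8%.

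**The case against.** **No strict contradiction.** Eligibility and dose are separate decisions. Every dose rule that names a visit names screening, and a passage that names no visit does not conflict with one that does. This stands: the text can be followed as written. What remains is that it can set dose from a reading that the protocol has replaced for eligibility.

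**Screening may be meant loosely.** Exclusion 5 also says at screening, yet Section 8.3.2.4 lets the baseline value replace it. A site could read the dose rule the same way. That is plausible, but the substitution is written for eligibility only. Section 10.10.3 shows that the protocol writes such tie-breaks where it wants them (there for the antigen test).

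**Sites dosing the same readings differently.** A reader might infer this. The documents do not show it. Containers are assigned through the IRT, the reduced tier has its own tablet mix, and Section 6.1.1 sends further dosing instructions to the product manual. The tier may be fixed centrally.

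**A number of wrongly dosed participants.** A reader might multiply the shares above by 411. The documents give no eGFR distribution, no share tested on both days and no data on one-day change, so no count is supported.

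**Full dose for someone below 30 at screening who recovers to 30 or above.** The literal default would be 300 mg. However, Exclusion 5 and the bar on rescreening in Section 5.4 make it doubtful that such a person would be enrolled.

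**Limited benefit.** Screening falls within 24 hours before randomization, and with stable function the later value is no more accurate. This stands and keeps the point minor.

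**Conclusion.** The wording mismatch holds with high confidence: a repeated baseline creatinine decides eligibility, the two dose rules that name a visit use screening, and nothing in the protocol or SAP extends the baseline rule to dose. That confidence does not extend to dosing in practice, which depends on the IRT and the product manual.

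The effect is confined to participants on active drug who are tested on both days and whose readings fall on either side of 60. The gain from a change is one consistent rule, plus a better-matched dose if kidney function truly changes before the first dose. The size of that second gain rests wholly on assumptions.

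A reader might also infer that the efficacy result is at risk. It is not: the mITT analysis compares randomized arms, dose tier is not in the primary model, and sample size, power and alpha do not depend on it. Severity is minor; this is a cheap improvement.

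**What to change.** 1. In the Dosage Level row of Section 6.1 and in Section 6.1.1, replace the reference to screening with: *at the most recent pre-dose point-of-care assessment (baseline if performed, otherwise screening)*.
2. In Section 8.3.2.4 and the Table 1 note, add *and nirmatrelvir dose* after the word eligibility.
3. Align Exclusion 5 in both Section 5.2 and the synopsis with the same rule.
4. Confirm that the IRT and the product manual use that value.

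The cost is wording in six places, best made with the next amendment because IRB/EC approval is needed, and possibly an IRT change, which cannot be judged from the documents. No new test, sample or visit is required.
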